2.1.3.2 Secondary efficacy endpoint(s)

The key secondary endpoint is the proportion of patients alive at Day 29.

Other secondary endpoints are:

1. Proportion of patients with one-point improvement from baseline in clinical status assessment at days 4, 7, 15, 21, 29 using the 7-point ordinal scale
2. Mean change in 7-point ordinal scale from baseline to days 4, 7, 15, 21, 29 (or until discharge)
3. Time to resolution of fever defined as body temperature ($\leq 36.6^{\circ}\text{C}$ [axilla], or $\leq 37.2^{\circ}\text{C}$ [oral], or $\leq 37.8^{\circ}\text{C}$ [rectal or tympanic]) for at least 48 hours without antipyretics or until discharge, whichever is sooner
4. Time to resolution of fever (as defined above) and improvement in oxygenation (as defined below)
5. Days with fever ($>37.4^{\circ}\text{C}$ [axilla], or $>38.0^{\circ}\text{C}$ [oral], or $>38.4^{\circ}\text{C}$ [rectal or tympanic]) based on maximum value observed during a 24-hour period.
6. Time to change in National Early Warning Score 2 (NEWS2) from baseline
7. Time to NEWS2 of <2 and maintained for 24 hours
8. Mean change from baseline to Day 4, 7, 15, 21, 29 in NEWS2
9. Time to improvement in oxygenation (SpO₂/FiO₂ of 50 or greater) compared to the nadir for at least 48 hours, or until discharge, whichever is sooner
10. Alive off supplemental oxygen at Day 29
11. Days of hypoxemia (SpO₂ $<93\%$ on room air, or requiring supplemental oxygen, or mechanical ventilatory support)
12. Days of supplemental oxygen use
13. Days of resting respiratory rate >24 breaths/min (maximum value if recorded at more than once a day)
14. Time to saturation $\geq 94\%$ on room air
15. Ventilator free days in the first 28 days (to Day 29)
16. Initiation of mechanical ventilation, non-invasive ventilation, or use of high flow nasal cannula (for those not requiring these interventions at baseline)
17. Proportion of patients requiring rescue medications during the 28-day period
18. ICU status (among those not in an ICU at baseline, record if transferred to the ICU or the need to transfer to the ICU [if the ICU is not available])
19. Days of hospitalization among survivors

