2.4.4.1 Analysis of primary efficacy endpoint(s)

The primary efficacy analysis will be pairwise comparisons between sarilumab doses (400 mg and 200 mg) and placebo with respect to the primary endpoint, time to improvement of 2 points in clinical status assessment from baseline using the 7-point ordinal scale, using a log-rank test stratified by randomization stratum with treatment as a fixed factor in the mITT population. P-values for the pairwise comparison of each sarilumab dose versus placebo will be provided.

Hazard ratios for the estimation of treatment effect of each sarilumab dose compared to placebo will be provided using Cox proportional hazards model stratified by the randomization stratum with treatment as a covariate, along with 2-sided confidence intervals. Kaplan-Meier (KM) plot and the median time-to-improvement of 2 points will also be provided by treatment groups.

Superiority of sarilumab over placebo will be declared if the null hypothesis is rejected at the 5% (2-sided) significance level following the multiplicity control procedure specified in [Section 2.4.4.3](#).

Patients who have an improvement of 2-points in clinical assessment or discharge (other than death) will be considered as events, while patients who do not experience improvement of 2-points will be censored at the last observation time point. Patients who take rescue medication in the study without improvement of 2-points before that will be censored at the date of rescue medication started.

In addition, the proportion of patients with at least 2-point improvement from baseline at each day post-baseline will be provided using descriptive statistics. Graphical presentations (bar charts) will be used to examine trends over time.

The analyses using the log-rank test and Cox PH model specified above will be repeated for the severe patients and critical patients at baseline as recorded on CRFs.

Baseline clinical status is defined as the worse (lower) value of screening visit and Day 1 prior to dosing. If there is a tie, flag Day 1 as baseline. Baseline values are 2, 3, 4, 5, or 6. Values 1 and 7 do not apply (if 1 or 7 appear, then data query is needed.)

Post-baseline clinical status values range from 1 through 7 on ordinal scale and data will be as recorded on the ordinal scale eCRF.

Handling of death or discharge on clinical status assessment (post-baseline)

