Patients who achieved resolution of fever or discharge (other than death) will be considered as events, while patients who do not experience resolution of fever will be censored at the end of study. Patients who started rescue therapy or died in the study will not be considered as having an endpoint event and will be censored at the earlier date of death or rescue therapy start date. Patients who do not have fever at baseline will be censored at the first dose date.

Analysis of endpoint #5: the number of days with fever

Fever is defined as body temperature $>37.4^{\circ}\text{C}$ (axillary), or $>38^{\circ}\text{C}$ (oral), or $>38.4^{\circ}\text{C}$ (rectal or auricular).

The number of days with fever will be analyzed using the ANCOVA model with treatment group and randomization strata as fixed effects for patients alive by Day 29. The LS treatment mean difference from placebo with standard error, along with corresponding 95 % confidence interval and p-value will be provided.

Summary statistics with mean, median, standard deviation, minimum and maximum will be provided. Histogram will be provided to illustrate the distribution of days with fever.

In addition, the percent of days with fever ($100 \times$ number of days with fever divided by number of days of follow-up, defined as the earlier date of death or discharge or last visit up to Day 29) for all patients, will be analyzed using the ANCOVA model with treatment group and randomization strata as fixed effects.

Improvement in Oxygenation

Improvement in oxygenation is defined as increasing in SpO₂/FiO₂ of 50 or greater compared to the nadir SpO₂/FiO₂. Nadir SpO₂/FiO₂ is the nadir (lowest value) at any point in the study, and looking forward, an improvement in oxygenation is increase of 50 or greater from nadir value for at least 48 hours. If nadir is observed on 2 or more different days post baseline, the day of the first occurrence of nadir will be used.

Baseline SpO₂/FiO₂ ratio is defined as the last available ratio prior to first dose.

Post-Baseline SpO₂/FiO₂ ratio is defined as the worst (minimum) value in each day.

For derivation of FiO₂, please see conversion table in [Section 2.5.2](#).

***Analyses of endpoint #4: time to resolution of fever and improvement in oxygenation,
#9: time to improvement in oxygenation, and
#14: time to saturation $\geq 94\%$ on room air***

The analysis of these endpoints will be performed similarly to the primary endpoint.

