Patients who do not experience the event under analysis will be censored at the last observation time point. Patients who die or take rescue medication in the study without experiencing the event will be censored at the earlier date of death or rescue medication started.

***Analyses of endpoint #11: days of hypoxemia,
#12: days with supplemental oxygen use,
#13: days of resting respiratory rate >24 breaths/min, and
#15: ventilator free days in the first 28 days***

The analysis of these endpoints will be performed using the ANCOVA model with treatment group and randomization strata as fixed effects for patients alive by Day 29. The LS treatment mean difference from placebo with standard error, along with corresponding 95 % confidence interval and p-value will be provided. Patient discharged early will be considered as ventilator free until the next hospitalization (if applicable).

Summary statistics with mean, median, standard deviation, minimum and maximum will be provided. Histogram will be provided to illustrate the distribution.

In addition, the percent of days with each endpoint ($100 \times$ number of days with the endpoint divided by number of days of follow up, defined as the earlier date of death or discharge or last

visit up to Day 29) for all patients, will be analyzed using the ANCOVA model with treatment group and randomization strata as fixed effects.

Analyses of endpoint #10: % of patients alive off oxygenation at Day 29, and #16: % of patients with initiation of mechanical ventilation, non-invasive ventilation, or use of high flow nasal cannula, and

These endpoints will be analyzed using a Cochran-Mantel-Haenszel (CMH) test stratified by randomization strata. The difference in proportions of patients for each Sarilumab dose compared to placebo (sarilumab - placebo), along with associated 2-sided 95% confidence levels, and p-value will be provided.

Bar plots will also be provided to illustrate the difference among treatments.

NEWS2

Please find NEWS2 score calculation and details in [Section 2.5.2](#).

Analyses of endpoint #6: Time to change in National Early Warning Score 2 (NEWS2) from baseline, and #7: Time to NEWS2 of <2 and maintained for 24 hours

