The analysis for time to change in NEWS2 from baseline will be performed by evaluating the proportion of patients with clinical risk over time in each category (Low: 0-4; Low-medium: 3 in any individual parameter; Medium: 5-6; High: ≥ 7). The pattern of patients in the categories shifting from baseline and over time will be examined with no formal testing.

The time to NEWS2 < 2 and maintained for 24 hours endpoint will be analyzed similarly to the primary endpoint.

Patients who do not experience endpoint event under analysis will be censored at the last observation time point. Patients who die or take rescue medication in the study without experiencing the event will be censored at the earlier date of death or rescue medication started.

Analyses of endpoint #8: Mean change from baseline to Day 4, 7, 15, 21, 29 in NEWS2

Change from baseline in NEWS2 score at Day 4, 7, 15, 21, and 29 will be analyzed using an ANCOVA model with treatment group and randomization strata as fixed effects, and baseline value as a covariate. The least squares (LS) treatment mean difference from placebo with standard error, along with corresponding 95 % confidence interval and p-value will be provided. Graphical presentations (line plot with mean and error bar) will also be used to examine trends over time using mean values (\pm SE) and mean changes from baseline (\pm SE).

NEWS2 score at each day and their changes from baseline will be summarized for each treatment group through descriptive statistics including mean, median, standard deviation, minimum and maximum.

ICU use, rescue medication, hospitalization and other

Analyses of endpoint #17: % of patients requiring rescue medication during the 28-day period, #18: % of patients with ICU use (among those not in an ICU at baseline)

These endpoints will be analyzed using a CMH method stratified by randomization strata. The difference in proportions of patients for each Sarilumab dose compared to placebo (sarilumab - placebo), along with associated 2-sided 95% confidence levels, and p-value will be provided.

Bar plots will be provided to illustrate the difference among treatments. Summary of immunosuppressive medications used as rescue therapy over time will also be provided.

Analyses of endpoint #19: Days of hospitalization among survivors

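### For time to NEWS2 below 2 held for 24 hours (#7), the SAP's censoring rule leaves out live discharge, so read literally it censors patients because they recovered

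*SAP*

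**What the plan says.** **Definition of #7.** SAP section 2.1.3.2 lists "Time to NEWS2 of <2 and maintained for 24 hours". It has no discharge clause, and neither does #14 (saturation of at least 94% on room air). The definition of #9 (improvement in oxygenation) does end at discharge if that comes sooner, and #4 takes this over by reference.

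**Analysis of #7.** SAP section 2.4.4.2 says the "maintained for 24 hours endpoint will be analyzed similarly to the primary endpoint". It then sets its own rule: "Patients who do not experience endpoint event under analysis will be censored at the last observation time point". For death and rescue it adds: "Patients who die or take rescue medication in the study without experiencing the event will be censored at the earlier date of death or rescue". The rescue date meant is the day rescue treatment began.

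**Primary endpoint and fever.** In section 2.4.4.1: "Patients who have an improvement of 2-points in clinical assessment or discharge (other than death) will be considered as events". For #3 in section 2.4.4.2: "Patients who achieved resolution of fever or discharge (other than death) will be considered as events".

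**#4, #9 and #14.** "The analysis of these endpoints will be performed similarly to the primary endpoint", followed by "Patients who do not experience the event under analysis will be censored at the last observation time point" and the same rule for death and rescue. The working definition of oxygenation improvement in section 2.4.4.2 requires 48 hours and drops the discharge clause that #9 carries in section 2.1.3.2.

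**Data after discharge.** SAP section 1.1 says patients need not return after discharge. The Day 29 telephone contact covers status and re-admission, so it supplies no NEWS2 score.

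**The concern.** Kaplan-Meier and Cox methods assume that a patient censored on a given day has the same prospects as those still under observation. A patient discharged alive has generally done better than those who remain in hospital. If discharge censors such patients, the analysis treats them as though they would have recovered at the rate of those left behind.

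Endpoint #7 is exposed to this for two reasons. The criterion must hold for 24 hours, while several NEWS2 components (respiratory rate, pulse, blood pressure) are scheduled once a day until discharge. A patient who first scores below 2 on the day of discharge cannot show 24 hours. Supplemental oxygen alone also scores 2 points (SAP section 2.5.2), so nobody can qualify until oxygen is withdrawn, which may be shortly before going home.

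At stake are the medians, the Kaplan-Meier curves and possibly the hazard ratio for #7. Two programmers following the present text could also produce different results.

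**Working it through.** **1. Does the text settle it?** The two rules set side by side:

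| Endpoint | Refers to the primary analysis | Live discharge written as an event | Own rule for patients without the event |
|---|---|---|---|
| Primary | n/a | yes | yes |
| #3 fever | yes | yes | yes |
| #7 NEWS2 | yes | no | yes |
| #4, #9, #14 | yes | no | yes |

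For #3 the SAP uses the same reference to the primary analysis and still spells out discharge. The reference was therefore not relied on to carry the event rule. For #7 the SAP restates the rules for non-events, death and rescue, and leaves out only discharge.

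**2. Model for the size.** The documents give no figure for #7, so nothing can be reproduced for it. Assume a constant recovery hazard λ, where recovery means criterion met or discharged alive. A share q of recoveries are discharged before the criterion is documented. The documents give no q, so values from 10% to 40% are assumptions.

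- Hazard of a documented event: (1-q)λ
- Median with discharge censored: ln 2 / [(1-q)λ] = true median × 1/(1-q)
- Hazard ratio with discharge censored: true HR × (1 - q on sarilumab) / (1 - q on placebo)
- Share of events lost: q

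**3. Medians.**

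- q = 10%: 1/0.9 = 1.11, inflated by 11%
- q = 20%: 1/0.8 = 1.25, inflated by 25%
- q = 30%: 1/0.7 = 1.43, inflated by 43%

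To put this in days, borrow the primary endpoint's sample-size assumptions (SAP section 1.3: 45% and 70% improved at Day 15). The placebo median is 15 × ln 2 / (-ln 0.55) = 17.4 days, and the sarilumab median is 15 × ln 2 / (-ln 0.30) = 8.6 days. With discharge censored:

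| q, both arms | Placebo median (days) | Sarilumab median (days) |
|---|---|---|
| 0% | 17.4 | 8.6 |
| 10% | 19.3 | 9.6 |
| 20% | 21.7 | 10.8 |
| 30% | 24.8 | 12.3 |

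**4. Hazard ratio, taking a true value of 1.40.**

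| q sarilumab | q placebo | Estimated HR |
|---|---|---|
| 30% | 30% | 1.40 × 0.7/0.7 = 1.40 |
| 40% | 30% | 1.40 × 0.6/0.7 = 1.20 |
| 30% | 40% | 1.40 × 0.7/0.6 = 1.63 |

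In the first row recovery is 1.40 times faster on sarilumab and the ratio is still unbiased. Only a difference in q moves it.

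**The case against.** The strongest reply is that the SAP nowhere says discharge is censored. It says #7 is handled like the primary endpoint, where discharge is an event, and the quoted sentence concerns only patients without the event. That reading is possible. It cannot be relied on, because the same reference for #3 was followed by an explicit discharge rule. The last observation could also be taken to be the Day 29 call. That would keep discharged patients at risk, unrecovered, until Day 29, so it does not remove the problem. The SAP also carries missing NEWS2 components forward without limiting this to the hospital stay, which allows a further reading.

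Several stronger claims that a reader might infer are not supported:

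- **That the fastest recoveries are lost.** Anyone who meets the criterion in hospital is an event before discharge. Only patients who leave before it is documented are affected.
- **That faster discharge on sarilumab biases the effect towards none.** The share q must differ between arms. The documents give no reason to expect a difference in either direction.
- **That #14 has the same problem and needs the same remedy.** It has no maintenance period, so one reading is enough, and a saturation reading at discharge appears to be scheduled (the table is broken in the text available). Counting every discharge as an event would score patients sent home on oxygen as having reached 94% on room air.

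It also stands that counting discharge for #7 broadens an endpoint that the protocol defines without it.

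**Conclusion.** The point holds for #7 as an omission that should be closed. Under the literal reading, patients discharged alive before 24 hours of NEWS2 below 2 can be documented are censored because of recovery. Medians are then too long whenever q is above zero: by 11% to 43% for q from 10% to 30%. The hazard ratio is affected only if q differs between arms, and may move either way (1.20 or 1.63 from a true 1.40 in the examples). These sizes rest on constant hazards and on assumed values of q; with q = 0 nothing changes.

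For #4 and #9 the definition and the analysis text need to be aligned. For #14 the exposure is small. #6 shares a heading with #7 but is not affected, since no formal test is planned for it. A reader might infer that the trial's main conclusions are at risk. They are not: the hierarchy in SAP section 2.4.4.3 covers only the primary and key secondary endpoints, and neither uses this rule.

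**What to change.** In SAP section 2.4.4.2:

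- **#7:** state that discharge alive without prior rescue is an event on the discharge date, as for the primary endpoint and #3. Report the version that censors at discharge as a sensitivity analysis.
- **#4 and #9:** carry the discharge clause of section 2.1.3.2 into the working definition of oxygenation improvement and into the censoring paragraph.
- **#14:** state how discharge is handled, and do not count patients discharged on supplemental oxygen as having reached at least 94% on room air.

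The cost is about one sentence per paragraph and one extra analysis, with no new data collection. The downside is that #7 becomes a composite of criterion met or discharged, which includes patients who go home on oxygen. The sensitivity analysis shows how much depends on that. Because the protocol defines #7 without discharge, the change should be recorded in the SAP's table of modifications and made by the blinded team before the primary database lock.

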Analysis of days of hospitalization among survivors will be performed using the ANCOVA model with treatment group and randomization strata as fixed effects. The LS treatment mean difference from placebo with standard error, along with corresponding 95 % confidence interval and p-value will be provided.

Summary statistics with mean, median, standard deviation, minimum and maximum will be provided. Histogram will be provided to illustrate the distribution.

In addition, the percent of patients died or “on a ventilator”, off oxygenation, and discharged will be summarized by treatment overtime, respectively. The time from first dose to discharge will also be summarized.

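### The tested percentages for start of ventilatory support (#16) and ICU use (#18) have no rule for death, so by default a death without escalation scores the same as recovery without it.

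*SAP*

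**What the plan says.** **The endpoints.** SAP 2.4.4.2 lists "16: % of patients with initiation of mechanical ventilation, non-invasive ventilation, or use of high flow nasal cannula" under the same heading as #10, and lists "17: % of patients requiring rescue medication during the 28-day period" together with "18: % of patients with ICU use (among those not in an ICU at baseline". SAP 2.1.3.2 restricts #16 to patients off these supports at the start: "use of high flow nasal cannula (for those not requiring these interventions at baseline". It also widens #18 beyond actual transfer: "record if transferred to the ICU or the need to transfer to the ICU [if the ICU is not available".

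**The test.** For #17 and #18: "These endpoints will be analyzed using a CMH method stratified by randomization strata". #16 has the same stratified CMH test. All three are reported with a difference in proportions, a 95% confidence interval and a p-value. SAP 2.3.1.1 makes mITT the population for secondary efficacy endpoints.

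**Death.** No sentence says how to score a patient who dies without the event. The general rule for percentages in SAP 2.5.3 removes only patients with missing data. Elsewhere in SAP 2.4.4.2, death is dealt with in one of three ways:
- censoring at death: #3, #4, #7, #9, #14;
- restriction to survivors: the main analyses of #5, #11, #12, #13, #15, and #19;
- survival built into the endpoint: #10.

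The text under #19 adds a percentage who died or were on a ventilator, but it is descriptive: "off oxygenation, and discharged will be summarized by treatment overtime".

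**The concern.** Starting ventilatory support and entering intensive care are bad outcomes, so a lower percentage reads as benefit. Death without either is worse, yet it lowers the percentage in the arm where it occurs. A reader of the #16 or #18 table cannot tell whether an arm had fewer escalations because patients did better or because some died first.

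Such deaths are foreseeable. Protocol 2.1 justifies the survival endpoint by the risk of death from conditions that the primary endpoint does not capture, such as myocardial infarction or kidney injury.

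What is at stake is the reading of two stated secondary objectives, new ventilation and need for ICU. The primary and key secondary conclusions are not affected.

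**Working it through.** **The plan's own figure.** None is given for #16 to #18. The only design figure is at least 90% power for the primary endpoint (SAP 1.3), and it reproduces. HR = ln(0.30)/ln(0.55) = 2.014. Events by Day 15 = 80×0.45 + 160×0.70 = 148. Then z = √(148 × 1/3 × 2/3) × ln(2.014) − 1.96 = 2.06, which is 98.0% power. It does not bear on this point.

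**The mechanism.** Let *r* be the proportion with the event or death without it, set equal in both arms. Let *d*P and *d*S be the proportions who die without the event on placebo and sarilumab. With no death rule, the tested percentages are *r* − *d*P and *r* − *d*S, so:

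tested difference (sarilumab − placebo) = *d*P − *d*S

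The shift is minus the difference in deaths without the event. It has no fixed sign.

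**Inputs.**
- Arm sizes of about 160 per sarilumab dose and 80 placebo: SAP 1.3.
- Eligible share for #16 and #18: not in the documents. Assumed 60%, giving 0.6×80 = 48 and 0.6×160 = 96.
- *r* = 35%, and all values of *d*: assumed.
- Test: unstratified difference in proportions at two-sided 5%, as an approximation to the CMH.

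**Main case, 10% vs 5%.** The tested percentages are 25% vs 30%.
- SE = √(0.25×0.75/48 + 0.30×0.70/96) = 0.0781
- 0.05/0.0781 = 0.64
- P(Z > 1.96 − 0.64) = 9.4%, against 2.5% with no shift

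**Range, same formula, 48 vs 96, *r* = 35%.**

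| Deaths without event, placebo vs sarilumab | Tested percentages | Shift | Chance of a significant result in the direction of the shift |
|---|---|---|---|
| 5% vs 5% | 30% vs 30% | 0 | 2.5% each way |
| 4% vs 2% | 31% vs 33% | +2 points | 4.3% (against sarilumab) |
| 10% vs 5% | 25% vs 30% | +5 points | 9.4% (against sarilumab) |
| 12% vs 4% | 23% vs 31% | +8 points | 17.9% (against sarilumab) |
| 5% vs 10% | 30% vs 25% | −5 points | 9.2% (for sarilumab) |

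**Sensitivity to *r*, at 10% vs 5%.**
- *r* = 25%: SE = √(0.15×0.85/48 + 0.20×0.80/96) = 0.0657, giving 11.5%.
- *r* = 45%: SE = √(0.35×0.65/48 + 0.40×0.60/96) = 0.0851, giving 8.5%.

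**Does the missing-data rule help?** Take assumed counts of 24 events and 4 deaths without the event among 80 on placebo, and 40 and 16 among 160 on sarilumab (pooled two-proportion test).
- Deaths kept as non-events: 24/80 = 30.0% vs 40/160 = 25.0%, p = 0.41.
- Deaths dropped as missing: 24/76 = 31.6% vs 40/144 = 27.8%, p = 0.56.
- Death counted with the event: 28/80 = 35.0% vs 56/160 = 35.0%, p = 1.00.

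Dropping the deaths still leaves a difference where event-or-death is equal.

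**The case against.** **The SAP does not say that deaths are event-free.** Correct. A reader might infer a deliberate rule, but there is none. The non-event score is what results when a percentage with a fixed denominator has no rule for death. The defect is the silence and its default effect.

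**Death is already tested together with respiratory status.** This also stands. SAP 2.4.4.1 sets status to 1 at death and carries it forward, on a scale whose levels 2 and 3 are invasive ventilation or ECMO and non-invasive ventilation or high flow. That scale is tested as #1 (CMH) and #2 (ANCOVA). #10 requires survival, and Day 29 survival has its own CMH test. A reader might infer that only the untested died-or-ventilated summary combines the two, and that would be wrong. However, none of these measures new escalation or ICU use in patients free of it at baseline.

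**The literal objective is incidence.** In the main case the percentages escalated really are 25% and 30%. The 9% is a false-positive rate only if the target is event or death. That is fair as far as it goes. But a lower percentage produced by deaths is not evidence of less need for escalation, which is how the result would be read. For #17 the objection prevails: rescue is given at the physician's judgement (Protocol 6.6), and rescue or death would no longer answer the objective on rescue use.

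**Mitigations.** Deaths after escalation already count as events. #18 counts need for ICU when none is available. Criterion E 01 excludes patients judged unlikely to survive after 48 hours. These reduce the number of relevant deaths but do not set it to zero.

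**Standing.** #16 to #18 lie outside the hierarchy in SAP 2.4.4.3, so their p-values are nominal.

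**Conclusion.** The point holds for #16 and #18 as a cheap improvement. Followed as written, the plan can report a difference in escalation or ICU use that comes only from deaths without escalation. The shift equals minus the between-arm difference in those deaths. Under the assumptions shown (35% event or death in both arms, 48 vs 96 eligible), a 5-point imbalance raises the chance of a nominally significant result in the direction of the shift from 2.5% to about 9%. A 2-point imbalance gives about 4%, and no imbalance gives no shift. All of these rates are assumed.

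Two stronger readings are not supported. First, the bias need not favour sarilumab: more such deaths on placebo push the result against it. Second, the larger figures obtained with the full 80 and 160 patients (for example 13% at 10% vs 5%) do not fit #16 and #18, because both exclude patients already on support or in ICU at baseline.

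**What to change.** - **#16 and #18:** add event or death by Day 29 as the tested comparison, with the same CMH, strata and baseline restriction. Beside it, show by arm the planned percentage and the percentage who died without the event.
- **#17:** keep the planned percentage as the endpoint and report by arm the number and percentage who died without rescue. Do not replace it with a composite.
- **Timing:** record the change in the SAP's modification table before the primary database lock, made by blinded staff.

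**Cost.** A few sentences in SAP 2.4.4.2 and a few extra table rows. No new data are needed: vital status is collected daily until discharge and survival at the end of study (Protocol 1.3), and SAP 2.4.4.1 already names the sources of death dates. The protocol-defined percentages are still reported, and Protocol 9.4.3.1 asks only for a percentage with a 95% confidence interval for incidence data. The downside is that the composite mixes death with escalation, so it must not be shown without its components. Its p-values remain nominal, outside the hierarchy.
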